#### 4. MANAGEMENT OF ACUTE ANAPHYLAXIS

#### 4.1 Immediate intervention

- 1. Assessment of airway, breathing, circulation, and adequacy of mentation
- 2. Administer epinephrine intramuscularly every 5-15 minutes, in appropriate doses, as necessary, depending on the presenting signs and symptoms of anaphylaxis, to control signs and symptoms and prevent progression to more severe symptoms such as respiratory distress, hypotension, shock and unconsciousness

# 4.2 Possibly appropriate, subsequent measures depending on response to epinephrine

- (a) Place patient in recumbent position and elevate lower extremities
- (b) Establish and maintain airway
- (c) Administer oxygen
- (d) Establish venous access
- (e) Normal saline IV for fluid replacement

# 4.3 Specific measures to consider after epinephrine injections, where appropriate

- (a) Consider epinephrine infusion
- (b) Consider H1 and H2 antihistamines
- (c) Consider nebulized  $\beta 2$  agonist [e.g., albuterol (salbutamol)] for bronchospasm resistant to epinephrine

- (d) Consider systemic corticosteroids
- (e) Consider vasopressor (e.g. dopamine)
- (f) Consider glucagon for patient taking  $\beta$ -blocker
- (g) Consider atropine for symptomatic bradycardia
- (h) Consider transportation to an emergency department or an intensive care facility
- (i) For cardiopulmonary arrest during anaphylaxis, high-dose epinephrine and prolonged resuscitation efforts are encouraged, if necessary

Adapted from: Kemp SF, Lockey RF, Simons FE; World Allergy Organization ad hoc Committee on Epinephrine in Anaphylaxis. Epinephrine: the drug of choice for anaphylaxis. A statement of the World Allergy Organization. Allergy. 2008; 63(8):1061-70.

# Appendix G Restricted and prohibited medications

### **PROHIBITED AND RESTRICTED MEDICATIONS**

### Asthma medication restrictions

Medication	Prohibited/restricted	Details
Maintenance treatment with long-acting bronchodilators (including ICS/LABA combinations)	Restricted	Changes in dose and regimen should not be done from enrolment and throughout the study treatment (unless there is a medical need as judged by the Investigator) Usual ICS/LABA should not be taken prior to scheduled study visits defined in the protocol and home lung function assessments (to be administered once assessments are completed)
		Subjects should be instructed not to use their twice daily LABA within 12 hours of the scheduled site visit. For once daily LABA a 24 hour washout period is required Subjects will not need to washout of their asthma medications for unscheduled visits due to asthma
		worsening

Clinical Study Protocol Appendix G Drug Substance Tralokinumab (CAT-354) Study Code D2210C00014 Edition Number 1.0 Date 26 February 2015

Short acting β2-agonists (SABA)	Restricted	Regular scheduled use not allowed from enrolment through the study duration Rescue use of SABA administered via nebulization is discouraged, except as urgent treatment during an asthma exacerbation SABA should not be used within 6
		hours prior to scheduled study visits defined in the protocol and home lung function assessments with the exception of any unscheduled visits due to asthma worsening and home lung function assessments
Additional Maintenance Controllers	Allowed with restriction	Stable dose for 1 month prior to Visit 1; stable dose during the treatment period Subjects on theophylline should have blood concentration levels within therapeutic range documented before Visit 1
		Subjects should be instructed not to use additional once daily bronchodilators within 48 hours of the scheduled study visits defined in the protocol with the exception of any unscheduled visits due to asthma worsening
Short acting anticholinergics (e.g. ipratropium)	Restricted	Not allowed from enrollment and throughout the study as a rescue treatment for worsening asthma symptoms outside of managing an asthma exacerbation event
		May be used for managing an asthma exacerbation event

Long-acting β-agonists as a reliever (e.g. Symbicort Maintenance and Reliever Treatment)	Prohibited	Not allowed from enrolment and throughout the study duration
Zileuton	Prohibited	Not allowed 30 days prior to Visit 1;during treatment period

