## 5.1.10 Home PEF testing

An electronic hand-held peak expiratory flow (ePEF) meter will be provided to the subject at Visit 1. ePEF meter will be paired with an eDiary which will record, store and send the readings via a cellular network.

Home PEF testing will be performed by the subject in the morning upon awakening (prior to taking their AM asthma controller) and in the evening at bedtime (prior to taking their PM asthma controller). For details see Section 7.7.1.1 and Appendix G. Recording of home PEF should start from the evening of Visit 1 until the morning of Visit 9 (Week 12) using an ePEF meter device.

Subjects should perform 3 successive peak flow manoeuvres while sitting or standing, but in the same position at every testing; the highest of the 3 values will be captured for the morning and for the evening manoeuvres.

The Investigator/authorized delegate will check subject's adherence to correct use of the peak flow meter at each visit as shown in Table 1.

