## 5.1.12 Assessment of asthma exacerbation

Assessment of asthma exacerbation will be performed in accordance with the schedule provided in Table 1.

For the purpose of the study, an asthma exacerbation will be defined as a worsening of asthma that leads to any of the following:

- A temporary bolus/burst of systemic corticosteroids for at least 3 days to treat symptoms of asthma worsening; a single depo-injectable dose of corticosteroids will be considered equivalent to a 3-day bolus/burst of systemic corticosteroids
- An emergency room or urgent care visit (defined as evaluation and treatment for <24 hours in an emergency department or urgent care centre) due to asthma that required systemic corticosteroids (as per the above)
- An in-patient hospitalization (defined as admission to an inpatient facility and/or evaluation and treatment in a healthcare facility for ≥ 24 hours) due to asthma

Worsening of asthma is defined as new or increased symptoms and/or signs (examination or lung function) that can be either concerning to the subject (subject-driven) or related to an asthma daily diary alert (diary-driven). Baseline values for diary-driven alerts will be the mean of measures collected between Visits 1 and 2.

The eDiary will be programmed to alert both the subject and study centre when certain prespecified worsening thresholds are crossed including:

- Decrease in morning peak flow ≥20% on at least 2 consecutive days compared with baseline, and/or
- An increase in rescue medication use of 4 or more puffs, or use of one new or additional nebulized  $\beta 2$  agonist on at least 2 consecutive days compared with the average use during baseline, and/or

- An increase of 2 nocturnal awakenings due to asthma over a 7 day period compared with the average during baseline, and/or
- An increase in total asthma symptom score (the sum of day time [evening assessment] and night time [morning assessment] of at least 2 units above the baseline average or the highest possible score (daily score of 6), on at least 2 consecutive days

If an exacerbation event is not associated with deterioration in at least 1 of the pre-specified objective measurements, the Investigator will have to justify the decision for defining the event as an exacerbation and record it in the eCRF. Events that are not supported by any objective assessment will be deemed not to be a protocol-defined exacerbation.

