#### **Rescue medication**

The number of rescue medication inhalations (puffs) and nebulizer treatments taken will be recorded by the subject in the Asthma Daily Diary twice daily (i.e., in the morning and evening) beginning the evening of Visit 1 until the morning of Visit 9. The number of inhalations taken between the morning and evening lung function assessments will be recorded in the evening. The number of inhalations taken between the evening and the morning will be recorded in the morning.

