### 7.7.1 Restriction during and after the study

### 7.7.1.1 Asthma medication restrictions

### Use of short-acting β₂-agonists (SABA)

Regularly scheduled SABA use in the absence of any asthma symptoms is discouraged from enrolment (Visit 1) and throughout the study duration.

Prophylactic use of SABA (e.g., prior to planned exercise) if deemed necessary by the subject and the Investigator, may be used, but should **not** be recorded in the Asthma Daily Diary. Any such use should be documented in medical notes and recorded in the eCRF.

SABA via a metered dose device is permitted as needed for worsening asthma symptoms (i.e., rescue use) and will be recorded in the Asthma Daily Diary as number of inhalations.

Rescue use of SABA administered via jet or ultrasonic nebulization is discouraged, except as urgent treatment during an asthma exacerbation. Occasions where SABA was administered via nebulization will be recorded separately from metered dose inhaler inhalations in the Asthma Daily Diary.

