### **Restrictions prior to home PEF testing**

Subjects should avoid taking their morning asthma controller medication prior to the morning home PEF testing, and should conduct the evening home lung function testing before taking evening asthma controller medication.

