### Asthma medication restrictions for scheduled visits

Subjects should be instructed not to take their usual asthma controller medication prior to scheduled study visits (Except on visits when bronchoscopy is scheduled). Subjects should be advised to bring their scheduled asthma medications along with them to study site and take them after the study visit assessments as per Table 1 are complete. Following restrictions apply for scheduled visits:

- Use of SABA within 6 hours
- Use of twice daily LABA or ICS/LABA within 12 hours
- Use of once daily LABA within 24 hours
- Use of theophylline and once daily BD within 48 hours

If the above restrictions are not adhered to Investigator should reschedule the study visit. However, for Visits 4, 5, 7 and 8, Investigator can decide if the same restriction should apply.

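### Appendix G both restricts and exempts SABA before home lung function tests, and conflicts with Section 7.7.1.1 on regular SABA use: a minor point, but the texts must be reconciled

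*Protocol*

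**What the plan says.** **SABA before home lung function.** The SABA row of Protocol Appendix G applies a 6-hour withholding rule to scheduled study visits and to "home lung function assessments with the exception of any unscheduled visits due to asthma worsening and home lung function assessments". One sentence names home lung function first as covered by the rule and then as excepted from it.

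**Regular scheduled SABA.** The same Appendix G row states "Regular scheduled use not allowed from enrolment through the study duration". Section 7.7.1.1 states "Regularly scheduled SABA use in the absence of any asthma symptoms is discouraged".

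**What the body says about home PEF.** Section 5.1.10 directs the reader elsewhere: "For details see Section 7.7.1.1 and Appendix G". The home PEF paragraph of Section 7.7.1.1 speaks only of controllers: "Subjects should avoid taking their morning asthma controller medication prior to the morning home PEF testing", with a matching instruction for the evening. Section 7.7.1.2 lists "Use of SABA within 6 hours", but among the restrictions for scheduled visits.

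**Where this is used.** One eDiary alert in Section 5.1.12 is "Decrease in morning peak flow ≥20% on at least 2 consecutive days compared with baseline"; the alert baseline is the mean of measures between Visits 1 and 2. SAP Section 2.2 makes use of restricted medication outside the protocol's restrictions, during the randomized treatment period, an important protocol deviation.

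**The concern.** A site that follows the reference in Section 5.1.10 reaches one text that does not mention SABA before home PEF and another that contradicts itself. One site could tell subjects to withhold SABA before blowing and another could tell them it does not matter. Where it is left open, a subject's readings may be taken sometimes after SABA and sometimes not. That affects both the diary alert, which compares later mornings with a run-in mean, and the home PEF summaries.

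The second conflict is one of force and scope. Appendix G bars regular scheduled SABA without qualification; Section 7.7.1.1 discourages it, and only when symptoms are absent. A subject on regular SABA is outside the restrictions on one text and arguably inside them on the other. SAP Section 2.2 refers to the protocol's restrictions without saying which text governs, and SAP Section 6 does not mention the matter.

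**Working it through.** **Step 1: can another passage resolve the home PEF point?**

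| Text | Medication covered | Occasion covered |
|---|---|---|
| Appendix G, SABA row (rule) | SABA, 6 hours | Scheduled visits and home lung function |
| Appendix G, SABA row (exception) | SABA | Unscheduled visits for worsening, and home lung function |
| Section 7.7.1.1, before home PEF | Controllers only | Home PEF |
| Section 7.7.1.2 | SABA, 6 hours | Scheduled visits only |
| Section 5.1.10 | Refers to 7.7.1.1 and Appendix G | Home PEF |

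None does. The protocol gives no order of precedence between body and appendix. The appendix is dated 26 February 2015 and the revised body 15 January 2016, but neither says the later text prevails. The next Appendix G row, on additional controllers, has the exception for unscheduled visits without the home lung function phrase, so a drafting slip is likely. That does not tell a reader which half of the SABA sentence was meant.

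**Step 2: how far could mixed states move the PEF trigger?** The plan has no figure of its own to reproduce here. It also gives no PEF response to SABA, so the response r is an assumption. The nearest figure is the entry requirement of at least 12% reversibility, which is for FEV1. I take r = 5%, 12% and 20%.

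Let b be the SABA-free baseline PEF and x the true fractional fall. The trigger is reached when the later reading is at most 0.80 of the recorded baseline.

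- *Both readings in the same state:* the factor (1 + r) cancels, and x = 20%.
- *Only the later reading follows SABA:* b(1 − x)(1 + r) = 0.80b, so x = 1 − 0.80/(1 + r).
- *Only the baseline follows SABA:* b(1 − x) = 0.80b(1 + r), so x = 1 − 0.80(1 + r).

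| Assumed r | True fall needed, only later reading after SABA | True fall needed, only baseline after SABA |
|---|---|---|
| 5% | 1 − 0.80/1.05 = 23.8% | 1 − 0.80 × 1.05 = 16.0% |
| 12% | 1 − 0.80/1.12 = 28.6% | 1 − 0.80 × 1.12 = 10.4% |
| 20% | 1 − 0.80/1.20 = 33.3% | 1 − 0.80 × 1.20 = 4.0% |

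These are the extremes. The baseline is a mean over about two weeks, so a partial mix of states lies between the columns. The trigger can become harder or easier to reach, and nothing in the documents says which is more likely.

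**Step 3: can the state of a reading be recovered afterwards?** Not reliably. The diary holds puff counts per half-day, without clock times: "The number of inhalations taken between the evening and the morning will be recorded in the" morning. Section 7.7.1.1 also keeps prophylactic SABA out of the diary. Use within 6 hours of a given reading therefore cannot be identified.

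**Step 4: what depends on it?** SAP Section 4.2.8.5 summarises home PEF descriptively, with no model. SAP Section 4.2.6.3 only lists exacerbations. Efficacy uses the full analysis set regardless of protocol adherence, and there is no per-protocol set, so deviation status changes a table and a listing but no efficacy result.

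**The case against.** The strongest case on the other side is that this is a wording slip with little reach, and most of that case stands.

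- *The alert has other routes.* A reader might infer that a subject who takes rescue before blowing will escape the alert. The documents do not support that. Section 5.1.12 joins four triggers by and/or; the others are added rescue use, added nocturnal awakenings and a higher symptom score. Added rescue use counts towards its own trigger. Worsening may also be identified by the subject without an alert. And, as Step 2 shows, the PEF error need not mask a fall at all.
- *One deviation decision will be made.* A reader might infer that deviations will be counted in two ways. They could be classed either way, but SAP Section 2.2 has them identified and documented before unblinding, and SAP Section 4.2.2 adds physician review of disallowed medication before database lock. What is missing is the written rule for that decision.
- *Some mixing would remain anyway.* Rescue SABA is permitted as needed, so some home readings would follow SABA however the texts are reconciled.
- *The exception might mean home readings during a worsening.* That reading is possible, but it is not what the sentence says.

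What survives is that the instruction cannot be followed as written, and that no other passage repairs it.

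**Conclusion.** The point holds as a minor internal inconsistency. Appendix G contradicts itself on SABA before home lung function and differs from Section 7.7.1.1 on regular scheduled SABA. As a result, home PEF may be collected in mixed bronchodilator states, and a SABA deviation has no single definition.

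For an assumed PEF response of 5% to 20%, the true fall needed to reach the PEF trigger moves from 20% up to between 23.8% and 33.3%, or down to between 16.0% and 4.0%, depending on which reading follows SABA. These figures assume a constant proportional response and a complete contrast between baseline and later readings. The direction is undetermined, so a claim of systematic masking, or of bias in a known direction, would go beyond the documents.

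The primary biopsy endpoint, the secondary eosinophil and ECP endpoints and the sample size are unaffected.

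**What to change.** The sponsor should reconcile the Appendix G SABA row with Sections 7.7.1.1 and 7.7.1.2 on two points: SABA before home PEF, and regular scheduled SABA. SAP Section 2.2 should then state which protocol text defines a SABA deviation. I take no view on which rule is right. The cost is a protocol clarification, a note to sites and one sentence in the SAP.

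I would not add a home PEF summary that leaves out readings with reported rescue use. Half-day counts would flag use well outside 6 hours and would miss unrecorded prophylactic use. Such a summary would also select on a post-randomization outcome, removing symptomatic days, possibly to a different extent in each arm. If the removed readings counted as missing, the rule that more than 7 missing daily values voids a bi-weekly mean could cost frequent rescue users their Week 12 value.

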## **Other medication restrictions**

Medication	Prohibited/restricted	Details
Live Attenuated Vaccines	Prohibited	Not allowed 30 days prior to Visit 1; during treatment period and 4 months (5 half-lives) after the last dose of the investigational product
Inactive/killed vaccinations (e.g. inactive influenza)	Restricted	Allowed provided they are not administered within 5 days before or after any study visit
Any immunomodulators or immunosuppressives (including long-acting depo corticosteroids)	Prohibited	Not allowed 3 Months or 5 Half Lives (whichever is longer) prior to Visit 1; during treatment period; 3 Months or 5 Half Lives (whichever is longer) after the last dose of the investigational product
Blood products or immunoglobulin therapy	Prohibited	Not allowed 30 days prior to Visit 1; during treatment period
Any marketed (eg omalizumab) or investigational biologic treatment	Prohibited	Not allowed 4 months or 5 half-lives (whichever is longer) prior to Visit 1; during treatment period; 4 months or 5 half-lives (whichever is longer) after the last dose of the investigational product
Other investigational products (including investigational use of an	Prohibited	Not allowed 30 Days or 5 Half Lives (whichever is longer) prior to Visit 1; during treatment period

Medication	Prohibited/restricted	Details
approved drug)		
Allergen Immunotherapy	Restricted	Allowed if on stable therapy for at least 30 days prior to Visit 1; no anticipated changed during treatment period and provided there is a span of at least 5 days between the immunotherapy and IP administration
Herbal remedies for the treatment of allergic, inflammatory, or respiratory diseases	Prohibited	Not allowed 30 days prior to Visit 1;during treatment period
Roflumilast	Prohibited	Not allowed 30 days prior to Visit 1;during treatment period
Oral or ophthalmic non- selective β-adrenergic antagonist (e.g. propranolol)	Prohibited	Patients currently using any oral or ophthalmic non-selective β-adrenergic antagonist at the time of enrolment are not eligible for the study Not allowed during treatment period
Medications not currently licensed for use in the treatment of asthma, for example medications approved for Chronic Obstructive Pulmonary Disease and not part of current standard of care	Prohibited	Not allowed 30 days prior to Visit 1; Not allowed throughout the duration of the study

Clinical Study Protocol Appendix H		
Drug Substance	Tralokinumab (CAT-354)	
Study Code	D2210C00014	

## Appendix H Post-BD spirometry and FEV₁ reversibility assessment algorithm

# POST-BD SPIROMETRY AND $\mathsf{FEV}_1$ REVERSIBILITY ASSESSMENT ALGORITHM

- 1. Verify with the subject that the medication restrictions for performing spirometry assessment have been met. For details please see sections 5.1.8 and 7.7.1.
- 2. Complete the initial (pre-BD)  $FEV_1$  measurement (refer section 5.1.8).

The standard metered dose for each inhalation of bronchodilator in the reversibility assessment is salbutamol  $100\mu g$ .

Step 1: FEV₁ measurement after 4 bronchodilator inhalations

For administration of salbutamol, the subject will:

- i. Perform a gentle, complete expiration
- ii. Inhale Dose 1 of bronchodilator to total lung capacity (TLC) and hold their breath for 5-10 seconds before the subject exhales
- iii. Rest for approximately 30 seconds before the next dose
- iv. Repeat this for Dose 2, Dose 3 and Dose 4, resting for a further 15 20 minutes after Dose 4

After resting for 15 - 20 minutes FEV₁ is measured following the technique described in section 5.1.8.

If the inclusion criterion for reversibility is met ( $\geq 12\%$  and  $\geq 200$  mL) this is the end of the reversibility assessment. If it is not met the subject proceeds to Step 2.

Step 2: FEV₁ measurement following a further 2 (total of 6) bronchodilator inhalations

The subject will repeat the inhalation procedures for Dose 5 and Dose 6, resting for 15 - 20 minutes after Dose 6. (See Step 1 above for instructions).

After resting for the 15 - 20 minutes FEV₁ will be measured following the technique described in Section 5.1.8.

This is the end of the reversibility assessment if either of the following occur:

- the inclusion criterion for reversibility is met ( $\geq 12\%$  and  $\geq 200$  mL) or
- the incremental change in FEV₁ between Step 1 and 2 is ≤5% and the inclusion criterion is not met

Subjects proceed to Step 3 if the incremental change in  $FEV_1$  between Step 1 and Step 2 is >5% but the criterion for reversibility has not yet been met.

#### Step 3: FEV₁ measurement following a further 2 (total of 8) bronchodilator inhalations

The subject will repeat the inhalation procedures for Dose 7 and Dose 8, resting for 15 - 20 minutes after Dose 8. (See Step 1 above for instructions).

After resting for the 15 - 20 minutes FEV₁ will be measured following the technique described in Section 5.1.8.

The reversibility assessment is now complete.

V3a and V9 (EOT) Post-BD spirometry assessment will stop at the end of Step 1.
